### JAEB CENTER FOR HEALTH RESEARCH

622	
 
Adolescents: LPV-FVQ II, ViSIO-PRO
 

623	Children: LPV-FVQ II
624 625 626	• The PROs may be completed in person or remotely (phone or other remote methods) any time within six (6) months of the Baseline Visit (not required to be the same day as the rest of the Baseline Visit).
627	3. Skin biopsy (3mm punch skin biopsy)
628	• Ship to Johns Hopkins University Department of Genetic Medicine Research Lab
629	4. Spectral Domain Optical Coherence Tomography (SD-OCT)
630	Volume Scan
631	Vertical and Horizontal Scan
632	5. Axial Length and Corneal Curvature Measurements
633	6. Fundus Autofluorescence
634	7. Widefield color photo
635	8. Optical coherence tomography angiography (OCTA)
636	Ancillary test; may be waived with approval from the Coordinating Center
637	9. Red reflex photo
638	10. Full field Stimulus Threshold (FST)
639	11. Measurements to include:
640	• Weight
641	♦ Height
642	

643

## **Chapter 4: Follow-up Visits**

### 644 **4.1 Follow-up Visits**

645 Follow-up Visits for all vision cohorts will occur annually. The Baseline Visit date is considered

study day zero (0) from which follow-up visit windows are timed. The Follow-up Visit date will

be the date the Follow-up Visit testing procedures started. All Follow-up Visit testing procedures

will be completed on the same date other than the PROs as noted in **Section 4.4 Follow-up** 

649 **Procedures**.

### 650 **4.2 Target Timelines**

- Target dates and windows for each study Follow-up Visit for all vision cohorts are shown below.
- Dates and windows are timed from Baseline Visit Date. Visits will be scheduled in the target window.

### 654

Table 4-1. Schedule for Follow-up Visits

VISIT SCHEDULE	TARGET DATE	TARGET WINDOW (AROUND TARGET DATE)
12 Month Visit	52 Weeks	± 4 Weeks
24 Month Visit	104 Weeks	± 4 Weeks
36 Month Visit	156 Weeks	± 4 Weeks
48 Month Visit	208 Weeks	$\pm 4$ Weeks

655 656

Table 4-2. Schedule for Remote Blood Spot Collection

BLOOD SPOT SCHEDULE	TARGET DATE	TARGET WINDOW (AROUND TARGET DATE)
4 Months	17 Weeks	± 4 Weeks
8 Months	34 Weeks	± 4 Weeks
16 Months	69 Weeks	± 4 Weeks
20 Months	86 Weeks	$\pm 4$ Weeks
28 Months	121 Weeks	± 4 Weeks
32 Months	138 Weeks	$\pm 4$ Weeks
40 Months	173 Weeks	± 4 Weeks
44 Months	190 Weeks	$\pm$ 4 Weeks

The goal will be for all participants to complete all scheduled visits. However, participants who,

because of unforeseen circumstances, are unable or unwilling to return for all follow-up visits

659 will be permitted to return for key visits only as an alternative to withdrawal from the study.

660 Additional office visits may occur as needed.

## 661 **4.3 Food Record and Blood Sample Collection**

All participants will be asked to complete the blood sample collection as described below. 662 Clinical Site Coordinators will complete a Pre-Sample Collection Telephone Call four (4) to 663 ten (10) days prior to the scheduled sample collection date. For at-home samples, the Post-664 Sample Collection Telephone Call should be completed within one (1) day after the scheduled 665 sample collection date. Reference the GYROS Clinical Site Manual of Procedures for more 666 details. 667 (1) Participant Contact 668 The Clinical Site Coordinator will contact the participants (via phone or other 669 remote interface) four (4) to ten (10) days prior to the scheduled sample 670 collection date. The Pre-Sample Collection Telephone Call will include 671 instructions and reminders of: 672 • The next sample collection date. 673 674 Fasting instructions. 0 • Food record collection instructions *(if applicable; see Food Record* 675 instructions below). 676 For at-home sample collections the Clinical Site Coordinator will contact the 677 participants (via phone or other remote interface) after the scheduled sample 678 collection date, within one (1) day preferred. The Post-Sample Collection 679 Telephone Call will include the collection of: 680 • Information on the participant's last meal. 681 682 0 Completion of the blood spot sample. Completion of the Food Record. 0 683 (2) Food Record 684 Participants who indicated following an arginine-restricted diet at 685 Screening will be asked to complete a food record every four (4) months 686 between Baseline and the 48M visit. 687 • If a participant initiates an arginine-restricted diet after Screening, the 688 participant will complete a food record every four (4) months going 689 forward. 690 691 • If a participant following an arginine-restricted diet at screening stops following an arginine-restricted diet at any point in the study, the 692 participant will continue to complete the food record every four (4) 693 months. 694 ALL participants will complete the food record for the 48M visit. 695 The participants will complete the food record every day for three (3) days 696 prior to the fasting sample collection. 697

698 699 700	
 
The participant will digitally send (e-mail or text) a picture of the food record to the site and either mail the original food record document to the site or bring it to the site at their next visit.
 

701 702	
 
The Clinical Site Coordinator will transcribe the data from the food record on the FFB Study Website.
 

703 704 705	
 
A Central Dietitian Reviewer (CDR) will review food record on FFB Study Website to determine nutritional content. This information will be entered into the FFB Study Website.
 

706	(3) Sample Collection
707 708 709 710	
 
At the annual Follow-up Visits, the Clinical Site Personnel will collect one         
 
(1) fasting plasma sample on all participants and ship to KKI. The sample collection procedures are detailed in the GYROS Clinical Site Manual of Procedures.
 
 
 

711 712 713 714	At the annual Follow-up Visits, the Clinical Site Personnel will collect one (1) fasting blood spot fingerstick on all participants and ship to KKI. The sample collection procedures are detailed in the GYROS Clinical Site Manual of Procedures.
715 716 717	
 
At the annual Follow-up Visits, the Clinical Site Coordinator would request the most recent lab records with an albumin result if the participant indicated they are currently on an arginine-restricted diet.
 

 
718
 
719
 
720
 
721
 
722
 
723
 
	
 
Every four (4) months between annual Follow-up Visits, one (1) fasting blood spot fingerstick will be collected on all participants. The participant or caretaker will collect the sample and ship to the central laboratory, KKI. The blood spot collection kits and instructions will be provided. The sample collection procedures are detailed in the GYROS Clinical Site Manual of Procedures.
 

724	4.4 Follow-up Procedures
725 726 727 728 729	The following procedures will be performed at the Follow-Up Visits, unless otherwise specified. The testing procedures are detailed in the GYROS Clinical Site Manual of Procedures. An overview of the equipment and certification requirements for all testing is in Chapter 5.1: Study Procedure Requirements . All ocular testing will be performed in each eye, OD first and then OS. Follow-up visit procedures will last approximately seven (7) – eight (8) hours.
730	4.4.1 Follow-up Data Collection and Testing Cohorts 1 & 2
731	1. Medical updates to include:
732	• New or changed adverse events (AEs)
733	
 
New ocular procedures
 

734	
 
New or changed medications
 

735	• Request medical records and laboratory records if applicable.
736	2. Patient Reported Outcomes

737	
 
Complete at 24-Month and 48-Month Follow-up Visits Only
 

738	
 
Adults: PROMIS®-29, MRDQ, ViSIO-PRO
 

739	
 
Adolescents: LPV-FVQ II, ViSIO-PRO
 

740	Children: LPV-FVQ II
741 742 743	• The PROs may be completed in person or remotely (phone or other remote methods) any time within the Allowable Window of the associated visit, (not required to be the same day as the rest of the Follow up Visit).
744	3. Complete ophthalmic examination to include:
745	Slit lamp biomicroscopy
746	Indirect ophthalmoscopy
747	4. IOP
748	• IOP measurements will be taken prior to pupil dilation.
749	5. VA (including refraction, ETDRS, BRVT if needed, LLVA if needed)
750 751 752	• The visual acuity letter score will determine whether LLVA or BRVT will be performed. The criteria are defined in the GYROS Clinical Site Manual of Procedures.
753	6. SD-OCT
754	Volume Scan
755	Vertical and Horizontal Scan
756	7. Axial Length and Corneal Curvature Measurements
757	Complete at 24-Month and 48-Month Follow-up Visits Only
758	8. Fundus Autofluorescence
759	9. Widefield color photo
760	10. OCTA
761	• Ancillary test; may be waived with approval from the Coordinating Center
762	11. Red reflex photo
763	12. Full field Stimulus Threshold test (FST)
764	13. Static perimetry
765	14. Fundus guided microperimetry
766	15. Measurements to include:
767	• Weight
768	• Height
769	• Measured annually in participants <21 years of age at enrollment.

770 4	4.4.2 F	ollow-up Data Collection and Testing Cohort 3
771	1.	Medical updates to include
772		• New or changed adverse events (AEs)
773		New ocular procedures
774		New or changed medications
775		
 
Request medical records and laboratory records if applicable
 

776	2.	Patient Reported Outcomes
777		Complete at 24-Month and 48-Month Follow-up Visits Only
778		Adults: PROMIS®-29, MRDQ, ViSIO-PRO
779		
 
Adolescents: LPV-FVQ II, ViSIO-PRO
 

780		Children: LPV-FVQ II
781 782 783		• The PROs may be completed in person or remotely (phone or other remote methods) any time within the Allowable Window of the associated visit, (not required to be the same day as the rest of the Follow up Visit).
784	3.	Complete ophthalmic examination to include:
785		Slit lamp biomicroscopy
786		Indirect ophthalmoscopy
787	4.	IOP
788		• IOP measurements will be taken prior to pupil dilation.
789	5.	VA (including refraction, ETDRS, BRVT if needed, LLVA if needed)
790 791 792		• The visual acuity letter score will determine whether LLVA or BRVT will be performed. The criteria are defined in the GYROS Clinical Site Manual of Procedures.
793	6.	SD-OCT
794		Volume Scan
795		Vertical and Horizontal Scan
796	7.	Axial Length and Corneal Curvature Measurements
797		Complete at 24-Month and 48-Month Follow-up Visits Only
798	8.	Fundus Autofluorescence
799	9.	Widefield color photo
800	10.	OCTA
801		• Ancillary test; may be waived with approval from the Coordinating Center
802	11.	Red reflex photo
803	12.	FST

13. Measurements to include:
-------------------------------------

- 805 Weight
  - Height
- 806 807

• Measured annually in participants <21 years of age at enrollment.

### 808 4.4.3 Unscheduled Visits

809 Testing procedures at unscheduled visits are at the investigator's discretion. However, it is

810 recommended that procedures performed during these visits follow the standard protocol for

811 each procedure and be performed by certified personnel. Unscheduled visits will be recorded on

the FFB Consortium study website. Study images taken during unscheduled visits do not require

submission to the study website.

814

## 815 **Chapter 5: Testing Procedures and Questionnaires**

## 816 **5.1 Study Procedure Requirements**

- 817 The study procedure instructions are detailed in the **GYROS Clinical Site Manual of**
- 818 **Procedures**. An overview of the equipment and certification requirements for all testing are
- 819 provided in the table below.

Study Procedures	Description	Equipment Required (If applicable)	Site Personnel Delegation
Investigator taking overall responsibility for a visit	Oversees that consent process was performed in accordance with IRB/EC requirements; signs off on all eCRFs for a participant, eCRF edits, and protocol deviations.	N/A	Certified investigator
Coordinator taking responsibility for the visit	Oversees the data entry aspect of the visit; addresses protocol queries and signs off on deviations.	N/A	Certified coordinator
Informed Consent Form (ICF) Process	Explanation/review of study with the potential participant and/or signature of ICF.	N/A	Certified investigator as permitted by the IRB/EC
Signature of Informed Consent Form	The participant and/or LAR sign the ICF. The person obtaining the ICF will also sign.	N/A	Certified investigator as permitted by the IRB/EC
Data entry on study website	Data collected from the study participant will be directly entered on the FFB Study Website (strongly encouraged) or written on the paper CRF and transcribed on the FFB Study Website within seven (7) days.	Computer and internet connection	Certified coordinator or certified investigator with additional study website certification
Collect information regarding medical history, demographics, adverse events, medications	Sites will collect medical history, demographic information, adverse events, and medications from the participant during each visit. This information can be confirmed by requesting medical records if needed.	N/A	Certified investigator or coordinator
Patient Reported Outcomes	There will be a total of four (4) questionnaires. Three (3) for adults and one $(1) - two$ (2) for minors depending on their age.	Study will provide	Certified investigator or coordinator
Ocular Exam	Including slit lamp biomicroscopy and indirect ophthalmoscopy	Any equipment is acceptable	Certified investigator
ЮР	Measurement of the fluid pressure inside the eye.	Any equipment is acceptable	Clinical site personnel performing this test does not require a study

Study Procedures	Description	Equipment Required (If applicable)	Site Personnel Delegation
			specific certification. However, they must be trained and delegated by the PI per the SSDL.
Visual Acuity – Refraction	Refraction is done as a routine part of an eye exam to achieve best corrected visual acuity measures	N/A	Clinical site personnel certified for refraction
Visual Acuity – ETDRS	Traditional measure of central visual function that represents foveal cone function,	EVA system, ETDRS charts	Clinical site personnel certified for ETDRS
Visual Acuity – LLVA	LLVA tests vision function in low luminance conditions.	EVA system, or ETDRS charts 2.0 neutral density filter to be provided by study	Clinical site personnel certified for performing ETDRS is also certified to perform LLVA
Visual Acuity – BRVT	BRVT incorporates a three-level hierarchy for visual acuity testing better suited for low vision participants.	BRVT charts provided by study	Clinical site personnel certified for BRVT
Spectral Domain Optical Coherence Tomography - Volume Scan	Scans provide objective, non- invasive measures of retinal structure, including loss of inner/outer segment junction and have been shown to correlate with visual function in eyes with retinal degeneration	Heidelberg Spectralis	Clinical site personnel certified for SD- OCT
Spectral Domain Optical Coherence Tomography - Vertical and Horizontal Scan	Scans provide objective, non- invasive measures of retinal structure, including loss of inner/outer segment junction and have been shown to correlate with visual function in eyes with retinal degeneration	Heidelberg Spectralis	Clinical site personnel certified for SD- OCT and vertical and horizontal scan
ОСТА	Provides information on foveal avascular zone enlargement and decreased macular vascular density	Site must use pre-approved device.	Clinical site personnel certified for OCTA
Axial Length and Corneal Curvature	Axial length measures the distance between the anterior and posterior poles of the eye. Corneal curvature determines the power of the cornea.	Any equipment is acceptable	Clinical site personnel performing this test does not require a study

Study Procedures	Description	Equipment Required (If applicable)	Site Personnel Delegation
			specific certification. However, they must be trained and delegated by the PI per the SSDL.
Fundus Autofluorescence	Captures areas of absent autofluorescence which corresponds with areas of chorioretinal atrophy seen on clinical exam	Optos	Clinical site personnel certified for widefield fundus autofluorescence
Widefield color photo (UWF color)	Complementary imaging modality that delineates the borders of the atrophic lesions classically associated with GA	Optos	Clinical site personnel certified for widefield color photo
Red reflex photo	Captures the area and severity of posterior subcapsular cataracts commonly associated with GA	Digital camera capable of capturing external eye photos, Megapixels of >=3MP, Magnification of 30-40 degrees, Digital camera export in PNG, TIF, DICOM or BMP	Clinical site personnel certified for red reflex photo
Full field Stimulus Threshold test (FST)	Measures rod- and cone-mediated parts of the visual field	Diagnosys Espion	Clinical site personnel performing this test does not require a study specific certification. However, they must be trained and delegated by the PI per the SSDL.
Static perimetry (SP)	A static field of vision test involves illuminating an object that does not move in the patient's field of vision to evaluate the vision in this manner.	Octopus 900 Pro (GATE Protocol)	Clinical site personnel certified for SP

Study Procedures	Description	Equipment Required (If applicable)	Site Personnel Delegation
Fundus guided microperimetry (MP)	This test will map out how bright a spot needs to be for the participant to be see it at specific locations inside the eye.	MAIA	Clinical site personnel certified for MP
Kinetic Perimetry (KP)	A kinetic visual field test involves moving an object in and out of a patient's peripheral vision to find the edge of the patient's field of vision.	Any equipment is acceptable	Does not need to be performed by study certified personnel or recorded on the GYROS Study Staff Delegation Log as this is a historical test.
Three (3) day food record	A three-day food record is designed to get an accurate description of a participant's typical daily diet.	Source provided by the study	Certified investigator or coordinator
Blood sample collection: • Fasting plasma amino acids	The Amino Acids Analysis, Plasma is a blood test that measures 36 amino acids and intermediary metabolites.	N/A	Does not need to be performed by study certified personnel or recorded on the GYROS Study Staff Delegation Log.
Blood sample processing: • Fasting plasma amino acids	During centrifugation, the barrier gel rises to separate the heavier cell mass from the lighter liquid portion.	Calibrated centrifuge	Certified investigator, coordinator, or appropriately trained laboratory staff
Measurements: • Weight • Height	Collect the participants height and weight using a calibrated scale in the office. BMI is automatically calculated on the FFB Study Website.	Calibrated scale	Certified investigator or coordinator
Skin Biopsy (3mm punch skin biopsy)	The skin is performed by stabilizing the area with the thumb and forefinger and stretched slightly perpendicular to the skin tension lines. A punch is held perpendicular to the skin, and is rotated into the skin with a firm, constant pressure.	Kit provided by the study	Certified investigator
Participant Contact Reminders to complete the three (3) day food record	The Clinical Site Coordinator will complete a Pre-Sample Collection Telephone Call to the participants (via phone or other remote interface) four (4) to ten (10) days prior to the scheduled sample collection date.	N/A	Certified investigator or coordinator

Study Procedures	Description	Equipment Required (If applicable)	Site Personnel Delegation
	The Clinical Site Coordinator will complete a Post-Sample Collection Telephone Call for at-home samples within one (1) day after the scheduled sample collection date.		
Food Record Collection and transcription of data on the FFB Study Website.	The Clinical Site Coordinator will collect and transcribe the data from the food record on the FFB Study Website	N/A	Certified investigator or coordinator

## 820 **5.2 Questionnaires**

- 821 The following questionnaires will be administered in the study by a certified investigator or
- 822 coordinator. Each questionnaire takes about fifteen (15) minutes to administer.

Questionnaire	Туре	Description	Vision Cohort	Age
Michigan Retinal Degeneration Questionnaire (MRDQ)	Vision Function	The MRDQ is a psychometrically validated patient-reported outcome measure for inherited retinal degenerations questionnaire which consists of fifty-nine (59) questions measuring seven (7) unidimensional domains: central vision, color vision, contrast sensitivity, scotopic function, photopic peripheral vision, mesopic peripheral vision, and photosensitivity.	All	Adults >= 18 years
PROMIS-29® (Patient-Reported Outcomes Measurement Information System®)	Global physical, mental, and social health	The PROMIS®-29 contains items from seven PROMIS domains: depression; anxiety; physical function; pain interference; fatigue; sleep disturbance; and ability to participate in social roles and activities. The seven domains cover the most relevant areas of self- reported health for most people with chronic illness. There is also one 11- point rating scale for pain intensity.	All	Adults >= 18 years
Visual Symptom and Impact Outcomes Patient Reported Outcome (ViSIO-PRO)	Vision Function and HRQoL	The ViSIO-PRO is an instrument designed to assess visual function symptoms, impacts on functional vision, and impacts on wider health- related quality of life (HRQoL). It has been designed for completion by adolescents (12-17) and adults (18 +) with retinitis pigmentosa (RP).	All	Adolescents (12-17) and Adults (18+)
L. V. Prasad- Functional Vision	Vision Function	The LVP-FVQ-II questionnaire consists of twenty-three (23)	All	Children (<18 years)

Questionnaire (LVP-FVQ II)	questions. The questionnaire is used to assess self-reported difficulties in	
	performing daily tasks in children with visual impairment.	

823

# 824 Chapter 6: Unanticipated Problem and 825 Adverse Event Reporting

## 826 **6.1 Unanticipated Problems**

Site investigators will promptly report all unanticipated problems meeting the criteria below on
an eCRF. Sites overseen by the JCHR IRB must report Unanticipated Problems to the IRB
within seven (7) calendar days of recognition. For this protocol, an unanticipated problem is an
incident, experience, or outcome that meets all the following criteria:

- Unexpected (in terms of nature, severity, or frequency) given (a) the research
   procedures that are described in the protocol related documents, such as the IRB approved research protocol and informed consent document; and (b) the
   characteristics of the subject population being studied.
- Related or possibly related to participation in the research (possibly related means there is a reasonable possibility that the incident, experience, or outcome may have been caused by the procedures involved in the research).
- Suggests that the research places participants or others at a greater risk of harm than
   was previously known or recognized (including physical, psychological, economic, or
   social harm).
- 841 The CC will report to the IRB all unanticipated problems not directly involving a specific site
- such as unanticipated problems that occur at the CC or at another participating entity such as a
   laboratory.
- 844 These instances must be reported to the JCHR IRB within seven (7) calendar days of recognition.
- The Director of the Human Research Protection Program (HRPP) will report to the appropriate
- regulatory authorities and applicable relying IRBs if the JCHR IRB determines that the event
- indeed meets the criteria of an Unanticipated Problem that requires further reporting to fulfill the
- reporting obligations of the HRPP.

## 8496.2 Adverse Events

## **6.2.1 Definitions**

- Adverse Event (AE): Any untoward medical occurrence, including laboratory findings,
- associated with study procedures whether the event is considered related. Progression of GA
- retinal dystrophy including new or worsening of anticipated clinical signs or symptoms, which
- are collected and assessed as unequivocally associated with the disease progression should NOT
- be reported as AEs unless the disease progression is greater than anticipated in the natural course of the disease.
- Serious Adverse Event (SAE): Any untoward medical occurrence that results in any of the
   following outcomes:
- 859 Death.
- A life-threatening adverse event: (a non-life-threatening event which, had it been more severe, might have become life-threatening, is not necessarily considered a serious adverse event).

- Inpatient hospitalization or prolongation of existing hospitalization.
- A persistent or significant disability/incapacity or substantial disruption of the ability to conduct normal life functions.
- A congenital anomaly or birth defect.

An important medical event that may not result in death, be life-threatening, or require

hospitalization may be considered serious when, based upon appropriate medical judgment, they

may jeopardize the patient or subject and may require medical and surgical intervention to
 prevent one of the outcomes listed in this definition.

- 871 **Note:** As this is a Natural History Study, the Investigator(s) will make the categorical
- determinations of Adverse Events, as described above, and will report each determination to the Coordinating Center, as per data collection
- 873 Coordinating Center, as per data collection.

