## **6.2.2 Reportable Adverse Events**

- For this protocol, a reportable adverse event includes all events meeting the definition of an adverse event.
- All reportable Adverse Events whether volunteered by the participant, discovered by study

personnel during questioning, or detected through ophthalmological examination, laboratory test,

- or other means will be reported on an adverse event form online.
- 880 The purpose of AE collection for the GYROS study will be to provide historical controls for
- future clinical trials. As a no greater than minimal risk study, AEs do not require any specific
- reporting to regulatory or oversight bodies. However, each Principal Investigator is responsible
- for abiding by any other reporting requirements specific to their IRB or equivalent ethics
- 884 oversight committee

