## 6.2.3 Relationship of Adverse Event to Study Procedure

- The study investigator will assess the relationship of any adverse event to be related or unrelated to a study procedure by determining if there is a reasonable possibility that the adverse event may have been caused by the study procedure.
- To ensure consistency of adverse event causality assessments, investigators should apply the
- following general guideline when determining whether an adverse event is related:
- 891 Yes
- 892 There is a plausible temporal relationship between the onset of the adverse event and the study
- procedure, and the adverse event cannot be readily explained by the participant's clinical state,
- intercurrent illness, or concomitant therapies; and/or the adverse event follows a known pattern
- of response to the study procedure; and/or the adverse event abates or resolves upon
- discontinuation of the study procedure.
- 897 **No**
- 898 Evidence exists that the adverse event has an etiology other than the study procedure (e.g.,
- 899 preexisting medical condition, underlying disease, intercurrent illness, or concomitant
- 900 medication); and/or the adverse event has no plausible temporal relationship to study procedure.

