### 964 **7.1.2 Medical Conditions during the study**

In addition to conditions meeting the reporting requirements for an adverse event or as described above, the following medical conditions should also be reported: (1) new diagnosis of a chronic disease (i.e., not present at the time of enrollment), and (2) any medical condition that could affect the participant's ability to carry out any aspect of the protocol or could affect an outcome assessment. These will be reported as adverse events. See **Chapter 6.2 Adverse Events** for more detail.

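### The adverse event definition in Section 6.2.1 is tied to study procedures, which conflicts with the historical-control purpose in 6.2.2 and with 6.2.3 and 7.3, so minor acute background events may be under-collected or collected unevenly

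*Protocol*

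**What the plan says.** Section 6.2.1 (Definitions) describes an adverse event as an untoward medical occurrence, laboratory findings included, "associated with study procedures whether the event is considered related". It then excludes anticipated progression of the retinal disease, which should not "be reported as AEs unless the disease progression is greater than anticipated in the natural course of the disease". The serious adverse event definition in the same section begins "Any untoward medical occurrence that results in any of the" listed outcomes and mentions no procedure.

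Section 6.2.2 (Reportable Adverse Events) ties reporting to that definition: "a reportable adverse event includes all events meeting the definition of an adverse event". It also gives the reason for collecting the data: "The purpose of AE collection for the GYROS study will be to provide historical controls for" future clinical trials.

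Section 6.2.3 sets up the causality judgement: "The study investigator will assess the relationship of any adverse event to be related or unrelated to a study procedure". Its *No* class applies where "Evidence exists that the adverse event has an etiology other than the study procedure", with underlying disease and intercurrent illness among the examples, or where the event has no believable link in time to a procedure.

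Section 7.1.2 extends reporting beyond events that already qualify: "above, the following medical conditions should also be reported: (1) new diagnosis of a chronic" disease, and (2) any condition that could interfere with carrying out the protocol or with an outcome assessment. Both are to be recorded as adverse events. Section 7.3 has sites enter on the adverse event form any adverse event caused by a pregnancy.

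**The concern.** Historical-control rates for a future treatment trial must show what happens to these patients without the treatment: ordinary ocular and systemic events as they arise. Events linked to blood draws, fingersticks, skin biopsy or dilating drops are a small and special part of that. A definition whose qualifier is association with study procedures points sites towards the special part, while the stated purpose needs the whole.

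The definition governs what is recorded during the study. A background event that a site did not record cannot be recovered by any later analysis plan, so the wording has to be settled in the protocol. Section 1.6 lists uniform adverse event definitions across sites among its measures against bias. Section 9.3 names adverse events, with eligibility, as the data that matter most for site monitoring. If the definition can be read two ways, sites and monitors lack a common standard for what counts as a missed event.

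**Working it through.** No formula applies. The check is to set the passages side by side and see which events each one admits.

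**1. Does the relatedness clause cure the definition?** The words at the end of the quoted phrase appear to have lost *or not*. With them restored, an event would count whether or not it is judged related, but it must still be associated with study procedures. The qualifier remains.

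**2. Which passages fit a narrow reading?** Section 7.1.2 presents its two kinds of condition as additions to events already meeting the adverse event requirements. If every untoward occurrence already qualified, that addition would be largely redundant.

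**3. Which passages fit a broad reading?**
- Section 6.2.3: an adverse event with no believable link in time to any procedure can hardly be one associated with a procedure, yet a class is provided for it.
- Section 6.2.1: the exclusion of anticipated disease progression is needed only if non-procedural events otherwise count.
- Section 6.2.1: the serious-event definition has no procedure qualifier.
- Section 7.3: events caused by pregnancy are not procedural, yet are called adverse events.
- Section 6.2.2: the historical-control purpose.

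No single reading satisfies all of these passages.

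**4. What is left out on the literal reading?** Take five kinds of event through the text:
- Bruise after venipuncture: inside, under 6.2.1.
- New chronic disease: outside 6.2.1, brought in by 7.1.2(1).
- Acute ocular condition that could affect an outcome assessment: outside 6.2.1, brought in by 7.1.2(2).
- Acute illness leading to hospital admission: counted as inside, under the unqualified serious-event definition.
- Short, self-limiting illness between visits that affects neither the protocol nor an outcome: outside 6.2.1, not serious, not chronic, not covered by 7.1.2. Nothing brings it in, although 6.2.3 provides a class for it.

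The exposed group is therefore non-serious, non-chronic events that are unconnected with procedures and affect neither protocol conduct nor an outcome assessment.

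**5. How could readings diverge?** The note in Section 6.2.1 leaves adverse event determinations to the investigators. Section 2.1 plans about 12 sites and about 50 participants, an average of roughly four per site (50/12 ≈ 4.2). With so few participants, a handful of sites applying the narrow reading could change the overall rate of minor events.

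**The case against.** The best defence is that the protocol, taken as a whole, plainly means general adverse event collection. The relatedness clause would be pointless if only procedure-caused events counted. Sections 6.2.3 and 7.3, the progression exclusion and the serious-event definition all assume a broad scope. Section 6.2.2 accepts events however they come to light, and the outcome categories in Section 6.2.7 include death and stable chronic conditions. Section 7.1.2 already brings in all new chronic disease and many of the ocular events that matter most to a retinal trial. On this view the phrase in 6.2.1 is a slip that experienced sites would read past.

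Much of this stands. A reader might infer from 6.2.1 alone that only procedure-linked events are collected and that background events as a class would go unrecorded. The other sections do not support that. A reader might also try to size the gap by the share of follow-up days on which procedures take place. That share describes calendar time rather than events, and it says nothing about how many events a site would omit.

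The defence does not remove the conflict. The sentence that decides reportability still carries the procedure qualifier, 7.1.2 is worded as if that qualifier were meant, and nothing in the protocol tells a site which reading prevails.

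**Conclusion.** The concern holds as an internal contradiction in the collection rule. Section 6.2.1 cannot be reconciled with the purpose in 6.2.2, the *No* class in 6.2.3 or the pregnancy events in 7.3. The consequence is limited to minor acute events of the kind identified above, which may be under-collected or unevenly collected. How many would be lost depends on how sites read the text, and the protocol gives no basis for a number.

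Under-collection would lower the control rate, so a later trial that records all events would tend to look worse by comparison. A reader might go further and expect a false excess of events on treatment. That would require sites to take the narrow reading despite 6.2.3, and a future trial to use these rates without adjustment; the protocol establishes neither. The study's own objectives concern retinal, metabolic and patient-reported outcomes and are not affected. The point is still worth correcting now, because adverse event control data are a stated aim and events left unrecorded cannot be restored later.

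**What to change.** Reword the definition in Section 6.2.1 to: *any untoward medical occurrence in a participant during the study, including laboratory findings, whether or not considered related to a study procedure*. Keep the disease-progression exception. Align Section 7.1.2 so that its two kinds of condition are named as examples falling within the definition, not as additions to it. Sections 6.2.2, 6.2.3 and 7.3 then agree with 6.2.1 without change, and the historical-control purpose is kept.

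The collection period need not change: the visit schedules start adverse event collection at Baseline. Procedure-related events remain separable, because 6.2.3 already records relatedness. The cost is somewhat more adverse event forms at sites, plus the ethics review that Section 10.2 requires for any amendment. If participants have already entered follow-up, the date of the clarification should be recorded so that rates before and after it can be told apart.
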